Examination of potential confounders Rates of adverse events and medication adherence in the IBUD and placebo groups will be calculated and compared. Medication adherence will be assessed as a continuous variable: the proportion of twice-weekly urine drug samples positive for riboflavin (≥ 900 ng/ml riboflavin as determined via quantitative fluorimetry), and as a dichotomous variable: medication adherent ($\geq 80\%$ of twice-weekly urine drug screens positive for riboflavin). Adherence will also be assessed via qualitative measurement of IBUD and metabolites in urine and serum samples, which is the gold standard for assessing adherence in the IBUD group but is limited by the fact that assessment of adherence in the placebo group is not possible. Models for MA use outcomes will be repeated including the continuous measure of adherence as a co-variate. The models will also be run with the sample stratified as medication adherent versus non-adherent. As pre-treatment abstinence is an important predictor of treatment outcomes and medication response in stimulant dependence trials (Elkashef, Rawson et al. 2008, Bisaga, Aharonovich et al. 2010), the sample will be stratified by ability to achieve initial abstinence with CM during the two-week lead-in period to explore whether medication effects may differ in these subgroups.

Aim 2: To determine whether IBUD results in longer treatment retention than placebo among MA dependent participants.

Hypothesis 2: IBUD will result in significantly greater treatment retention than placebo

Analysis: The mean number of days retained, defined as the number of days from the start of study medication to the final clinic visit during the 12 week treatment period, will be compared for IBUD versus placebo via t-test. Cox proportional hazards model will be used to compare days retained for IBUD versus placebo controlling for co-variables including age, gender, and baseline MA use. These analyses will then be repeated with the sample stratified by ability to achieve initial abstinence with CM during the two-week lead-in period to explore whether medication effects may differ in these subgroups.

The following exploratory HIV-related aims will be address in the HIV positive participants.

Aim 3: To determine whether IBUD improves biological (CD4 count; HIV RNA) and neurocognitive outcomes more than placebo among HIV-positive MA dependent participants.

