Exploratory analyses Baseline neurocognitive functioning of participants will be described using results of the neuropsychiatric (NP) battery performed at baseline. Baseline to post-treatment changes in scores on tests in the NP battery will be calculated for IBUD and placebo groups. Effect sizes for IBUD on NP battery change scores will be calculated and used to determine whether future fully powered studies examining NP changes with IBUD are warranted. In addition, GEE models will be used to compare change in the brief serial weekly cognitive assessments (Balloon Analog Reaction Time task and Stop Signal test) during treatment with IBUD versus placebo. To explore whether severity/type of neurocognitive dysfunction at treatment entry mediates response to IBUD, baseline scores on NP assessments will be included as co-variables in the models assessing IBUD effects on MA use outcomes and treatment retention. Finally, potential effects of polymorphisms in dopaminergic genes and GDNF (Yoshimura, Usui et al. 2011), as well levels of inflammatory biomarkers and neurotrophic factors on treatment outcomes will be explored. The sample will be stratified by genotype for each SNP and changes in MA use and retention for IBUD versus placebo will be compared in these sub-groups. In addition, baseline versus post-treatment serum and plasma levels of inflammatory markers neurotrophic factors will be compared for IBUD versus placebo groups and by HIV serostatus. Correlation between early life stress measures and baseline severity of MA abuse as well as treatment outcomes, including potential early life stress-ibudilast interactions, will also be explored.

We recognize that the study is not powered to detect statistical significance in these analyses, especially if corrections for multiple testing are employed (Benjamini and Hochberg 1995) and as a result these analyses are by design for exploratory purposes only. Still we feel that including these probes of potential IBUD mechanisms of action within the context of this early clinical trial is important in that the results may bolster any observed effects of IBUD on MA use outcomes and direct the design of subsequent adequately powered confirmatory phase III trials.

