Power calculations: Power is calculated (Figure 5) for the primary study outcome: the proportion of participants achieving MA abstinence during the final two weeks of treatment (weeks 11 and 12) in the IBUD versus placebo group. This is the FDA-preferred outcome for stimulant pharmacotherapy trials and was used in a previous study that found an effect size of 0.5 for bupropion relative to placebo for MA dependence (Elkashef, Rawson et al. 2008). For a Fischer's exact test comparing the proportion achieving abstinence during final two weeks on IBUD versus placebo, with an effect size similar to that in the previous bupropion trial (0.5), a one-tailed test assuming IBUD will be superior to placebo, and an $\alpha = 0.05$, 55 participants are required in each group (total N = 110) to achieve 80% power. Our total sample size of 140 exceeds 80% power. Note that the use of the outcome variable abstinent during the final two weeks of treatment accounts for attrition as participants who fail to complete the trial fail to achieve urine drug screen confirmed abstinence during the final two weeks (i.e. missing considered non-abstinent). This is a conservative approach but appropriate as an effective medication would be expected to sustain patients in treatment for the allotted time in addition to facilitating abstinence as longer treatment retention and treatment completion are strong predictors of superior long-term outcomes and sustained abstinence (Ahmadi, Kampman et al. 2006, Hillhouse, Marinelli-Casey et al. 2007).

Figure 5: Power by total sample size (IBUD plus placebo) calculated with G*Power 3.1.0 (Faul, Erdfelder et al. 2007).

References:

- Ahmadi, J., K. Kampman and C. Dackis (2006). "Outcome predictors in cocaine dependence treatment trials." Am J Addict **15**(6): 434-439.
- Alhassoon, O. M., R. M. Dupont, B. C. Schweinsburg, M. J. Taylor, T. L. Patterson and I. Grant (2001). "Regional cerebral blood flow in cocaine- versus methamphetamine-dependent patients with a history of alcoholism." The international journal of neuropsychopharmacology / official scientific journal of the Collegium Internationale Neuropsychopharmacologicum **4**(2): 105-112.

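### Effect modification by baseline cognition is analysed with main-effect covariates, and by lead-in abstinence and genotype with separate strata; no treatment-by-factor estimate is planned for any of the three

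*Combined protocol and SAP*

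**What the plan says.** Three parts of the Data Analysis section ask whether the effect of ibudilast (IBUD) depends on a baseline factor.

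- **Cognition** (Exploratory analyses). To explore whether dysfunction at entry "mediates response to IBUD, baseline scores on NP assessments will be included as co-variables in the models assessing IBUD effects". The models meant are those for methamphetamine (MA) use and for retention. No treatment-by-score term is mentioned.
- **Lead-in abstinence** (Examination of potential confounders). Participants are split by whether they stopped using MA under the lead-in incentives, and the arms are compared in each group to see if the effect is different. The Aim 2 retention analyses are repeated in the same strata.
- **Genotype** (Exploratory analyses). "The sample will be stratified by genotype for each SNP and changes in MA use and retention for IBUD versus placebo will be compared". This covers the seven SNPs of Table 3.

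The same Exploratory analyses paragraph does name interactions between early life stress and ibudilast. It is the only modifier for which the plan names one.

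Two statements bear on weight. The Exploratory analyses are declared underpowered and exploratory by design. Lead-in abstinence is listed in the Research Plan among the pre-specified subgroups for secondary analysis, so it falls outside that disclaimer.

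**The concern.** The two methods fail in different ways.

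A baseline score entered as a covariate shows whether people with better scores do better. It does not show whether IBUD works better or worse in them. Carried out exactly as written, the cognition analysis gives no information on its own question. The word mediates adds to the confusion: a variable fixed before randomisation cannot lie on the path from treatment to outcome, so the question is one of moderation.

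Stratified analyses do give an effect estimate in each stratum, but the plan states no comparison between them. The strata are smaller than the trial and unequal in size, so their p-values will often disagree even when the effects do not. For lead-in abstinence, a pre-specified secondary analysis, the report could then suggest a subgroup difference that is only noise. For cognition and genotype, the plan says that its probes of mechanism may shape later phase III trials.

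**Working it through.** **1. The plan's own figure.** Power calculations: "For a Fischer's exact test comparing the proportion achieving abstinence during final two weeks on IBUD versus placebo", "a one-tailed test assuming IBUD will be superior to placebo", alpha 0.05, effect size 0.5; "55 participants are required in each group (total N = 110) to achieve 80% power". The scale of the effect size and the placebo rate are not given. Reading 0.5 as Cohen's h (assumption), exact one-sided Fisher power at 55 per arm is 78.5%, 79.1%, 79.1% and 78.5% for placebo rates of 0.30, 0.35, 0.40 and 0.45. The n needed there is 56–57, so the figure reproduces closely. At 70 per arm power is 86–88%. The sample size is not in dispute.

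**2. Covariate versus interaction.** Let T be treatment and X a baseline score.
- As planned: logit p = b0 + bT·T + bX·X. The treatment effect is bT at every X.
- Needed: logit p = b0 + bT·T + bX·X + bTX·T·X. The treatment effect is bT + bTX·X.

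Take a crossover moderator with bX = −0.5 and bTX = 1.0 per SD (assumptions). The slope on X is −0.5 on placebo and −0.5 + 1.0 = +0.5 on IBUD. These roughly cancel in the planned model. In 1,500 simulated trials per case, the share significant at 5% was:

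| Truth | N | Covariate term | Interaction term |
|---|---|---|---|
| Crossover moderator | 85 | 4% | 53% |
| Crossover moderator | 140 | 5% | 78% |
| Prognostic only (log-OR 0.8 per SD) | 85 | 90% | 4% |
| Prognostic only | 140 | 99% | 4% |

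The covariate term misses a real moderator and is significant for a score that moderates nothing.

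**3. Strata with an identical effect.** The documents give neither stratum sizes nor rates. Assumptions: abstainers are 28, 42 or 56 of 140; placebo success is 40% in abstainers and 14% in the rest; the odds ratio is the same in both; arms are equal; the test is a two-sided 5% z test in each stratum. With powers a and b in the two strata,

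P(exactly one significant) = a(1 − b) + b(1 − a).

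Example, odds ratio 3, strata 28/112: IBUD success is 66.7% and 32.8%, a = 0.265, b = 0.669, giving 0.265 × 0.331 + 0.669 × 0.735 = 0.579.

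| Common odds ratio | 28/112 | 42/98 | 56/84 |
|---|---|---|---|
| 1 (no effect) | 9.1% | 10.1% | 9.7% |
| 1.5 | 17.9% | 19.3% | 19.4% |
| 2 | 35.0% | 35.6% | 36.2% |
| 3 | 57.9% | 52.1% | 49.9% |

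These are exact enumerations; simulation of the same scenarios with an effect gave 18–20%, 35–37% and 50–58%. A one-sided 5% test gives 44–45% at odds ratio 2 and 46–56% at 3. A correctly specified interaction test would flag a difference in about 5% of such trials.

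**4. Genotype cells.** Rare homozygotes expected among 140 = 140 × Table 3 frequency: rs12364283 1.4 (0.01), rs1076560 2.8 (0.02), rs2283265 4.2 (0.03), rs6265 4.2 (0.03), rs1800497 7.0 (0.05). These are before splitting by arm. The other two SNPs are better filled: rs2910704 15.4 (0.11), and rs6277, smallest cell, 23.8 (0.17). Table 3 is footnoted as HapMap CEU, so these counts are indicative only for this sample.

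**5. What an interaction term can deliver.** On the h scale SE = √(2/n1 + 2/n2), with n1 and n2 the stratum sizes per arm. The difference detectable with 80% power, two-sided 5%, is (1.960 + 0.842) × SE.
- N = 140, split 50/50: √(2/35 + 2/35) = 0.338, so 0.95.
- N = 140, split 20/80: √(2/14 + 2/56) = 0.423, so 1.18.
- N = 85, split 50/50: √(4/21.25) = 0.434, so 1.22.

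For a difference of 0.5, as large as the whole design effect, power at N = 140 with a 50/50 split is 32%.

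**The case against.** The strongest reply is that the cognition and genotype analyses are openly exploratory and unpowered, that the lead-in analysis is also worded as exploration, and that no efficacy decision rests on any of them. That stands and limits the severity. It does not rescue the cognition analysis, because the disclaimer concerns power, whereas the planned coefficient estimates a different quantity at any sample size.

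Several stronger readings are tempting, but the documents do not support them.
- A reader might infer that stratification cannot answer the question. It can, if the stratum estimates are formally compared; the plan does not say that they will be.
- A reader might infer that the trial will announce false subgroup effects. The percentages above matter only if someone reads discordant p-values as a difference, and the plan states no such rule. They also depend on the assumed effect, falling to 9–10% with none, and use a simple z test where the plan has adjusted logistic, GEE and Cox models.
- A reader might infer that a spurious lead-in subgroup would steer phase III. The phase III sentence concerns the mechanistic probes in Exploratory analyses, not the lead-in stratification.
- A reader might infer that the genotype strata are nearly empty throughout. This applies only to the rare homozygotes of five of seven SNPs, and only if three levels are used, which the plan does not specify.

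It is also fair to say that interaction tests here have little power and do not settle multiplicity across many scores and seven SNPs. That argues for reporting estimates with intervals, not for omitting the term. Naming an interaction for early life stress suggests incomplete wording, not ignorance of the method.

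**Conclusion.** The point holds, at moderate weight. For cognition the stated method does not address the stated question, and this follows from the model form without any numerical assumption. For lead-in abstinence and genotype, a between-stratum comparison is missing. Its practical size for lead-in abstinence is the 18–58% chance of discordant significance under a common odds ratio of 1.5 to 3, conditional on the assumed placebo rates, stratum sizes and two-sided test. For genotype, five of seven SNPs would have about 1 to 7 rare homozygotes if the reference frequencies applied. Nothing here touches the primary comparison or the planned 140.

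**What to change.** Fit one model per question, with the factor's main effect and a treatment-by-factor term.
- **Lead-in abstinence:** use the week-2 urine definition in Randomization Procedures, and include the term in the Aim 1 models and the Aim 2 Cox model.
- **Cognition:** treatment by baseline NP score, in the 85 participants who received the full battery. The MoCA continued for everyone, so that score can use the whole sample.
- **Genotype:** treatment by genotype, with additive or carrier coding.

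Report each interaction estimate with its 95% confidence interval, take the subgroup effects from the same model, and replace mediates with moderates. State that these are low-power estimates, that a null interaction does not show equal effects, and that the cognition and genotype analyses remain exploratory.

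The cost is SAP wording only: same data, same model families, no change to sample size.

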APPENDIX I

Standard Operating Procedure: Managing Behavioral Disruption in Methamphetamine Dependent Participants

OVERVIEW

PURPOSE: The purpose of this Standard Operating Procedure is to guide behavior of staff members in responding to behavioral disruptions on the part of participants who are methamphetamine dependent and who are either inpatient or outpatient study participants.

BACKGROUND: For the most part, methamphetamine dependent participants in outpatient studies are managed behaviorally in the same way as other participants in hospital studies. Predictability and calmness on the part of staff members will aid in keeping drama to a minimum, independent of whether the participant is methamphetamine dependent. Indeed, there is little to become concerned about in managing behavioral disruption from patients in studies of medications for methamphetamine dependence. Much of the skills necessary for managing participants who occasionally become disruptive during the hospital inpatient stay already exist in good measure among the staff. For example, if a methamphetamine dependent participant becomes argumentative with a staff member, that individual can ask the participant to calm down and that he may want to return to a room until he is less upset.

MANAGING MINOR BEHAVIOR DISRUPTIONS

Participants in this study will remain in the trial for a total of 18 weeks. In that time, some minor behavioral disruptions may occur. These behavioral disturbances will be managed successfully primarily by maintaining a general calm demeanor and using reasoning with the participants. Becoming upset in response to the patient's actions will generally exaggerate the crisis.

Signs: Participant's verbal and physical behaviors are the first clues of mild behavioral disruption.

- Participant becomes argumentative or complains about details of the clinic, the study or his life.
- Tone of voice is urgent, but generally not rude.
- Participant negotiates effectively with staff members who seek to resolve the disruptions.
- There is little indication participant will become physically assaultive.
- Participant is not being flagrant in other aspects of his behavior.

Using a calm demeanor, there are several responses you can use to successfully resolve a minor behavioral disruption caused by a methamphetamine dependent patient:

- Tell the participant you are willing to hear his complaint, but that you can do that only if he calms down.
 - When the participant calms down, *listen* to what s/he is saying and if possible, work with the participant to resolve the problem being expressed.
- Calmly ask the participant to remove him/herself from general community for a period (e.g., "time out" in a room) until his mood is calm and he can return to the community to discuss the problem.
- Ask if there is something that could be helpful to the participant in managing his upset mood (for example, food, snacks, movie, internet, cell phone).
- Check if the participant is experiencing tobacco withdrawal and whether he would like to be accompanied for a smoking break.

MANAGING MODERATE BEHAVIOR DISRUPTIONS

Signs: It is likely that one or two moderate behavior disruptions will occur as we complete 140 participants in this protocol. These disruptions are likely to involve display of strong and immediate concerns/desires to leave the clinic and to quit the study. You will be able to tell this is different than a minor disruption as you will find it difficult to "talk the participant down" or to get him to change his mind. It is unlikely that such moderate behavioral disruption will involve any threats of violence to staff or to self. It is far likelier that the participant will demand to be let out of

the unit (withdraw study consent). Still, if the participant threatens to leave the unit, it is critical that you reach [name], [name] or [name] immediately.

MANAGING SEVERE BEHAVIOR DISRUPTIONS

Signs: Severe behavioral disruption is rare and obvious. Signs of severe behavioral disruption include extreme agitation (beyond being upset), threats, self-injurious behavior etc.

For managing severe behavior disruptions, the main issue is to maintain safety for the participant and the clinic.

If there are concerns of threats to self/others, the Distress Protocol is activated (see below).

If the situation is not sufficiently severe to summon security/police (e.g., participant destroys property, but is not a threat to self/others), manage as a moderate behavioral disruption above and get in touch with one of the study investigators to manage staff and participant ASAP.

DISTRESS PROTOCOL

Signs: Subjects give clear signs when they are a danger to themselves or to someone else. These include but are not limited to:

- They tell you they have thoughts about killing you, killing themselves, or killing someone else.
- When a subject endorses item 3 of the HAMD with 2 or greater.
- When a subject has a total HAMD score greater than 17.
- Sometimes a family member or friend will tell you the subject is talking about impulsive actions against self/others.

When **any sign** like this occurs, the following distress protocol is implemented:

- 1) Inform the subject you are seeking assistance, especially if the subject uses language that references wishes to die, thoughts of being better off dead, no more reason to live, threats to kill you or any person who is identifiable (i.e., a named individual – not just a vague reference such as “any A-hole who gets in my way today”), etc.
- 2) **Immediately** notify the study clinician and request a licensed mental health provider be called. Once a staff member decides there is reason to initiate contact with a responsible clinician, contact must be **immediate** and follow through must be **complete**. It is critical that staff continue contacting study Investigators until someone is located and a licensed clinician is on-site to speak with the distressed subject. Distressed subjects must be evaluated by a licensed clinician with **one hour** of discovery.
 - a. **Highest Levels of Distress:** In cases in which a licensed clinician determines that immediate intervention is required to manage a subject’s extreme distress (e.g., that the individual is making an unambiguous threat to the safety of himself or to an identifiable intended victim), immediate steps will be taken to arrange for an involuntary hold at the Psychiatric ER to guarantee the subject’s physical safety and/or the physical safety of an identifiable intended victim. In the event that an identifiable intended victim is named and clinical staff determine the threat to be credible, the information regarding the threat and the intended victim’s identity will be provided to the police. In keeping with laws following Tarasoff requiring a counselor to warn an intended victim of a potential threat to their physical safety, clinical staff also will make contact with the identifiable intended victim and inform the individual that a credible threat to his life has been made by the distressed subject and that the individual should take appropriate measures to ensure his physical safety.
 - b. **Moderate Level of Distress:** For subjects who are assessed as clinically distressed, but not in need of emergency intervention or containment, the clinician will speak briefly with the subject and inform him that we require the subject to freely engage a “no suicide/no homicide” contract. This type of contracting procedure is standard to psychological practices in managing distressed subjects and is identical to the procedures in use in our clinical research projects for the past 12 years. Distressed subjects who receive this distress evaluation experience the procedure not as “coercive,” but instead find it reassuring that the level of distress they report is recognized and addressed. The counseling and contracting process also signals to the subject the seriousness the team places in keeping subjects oriented toward health and away from injurious behaviors. Observing the distressed subject’s reaction after completing a clinical assessment and after informing him we wish to enter a commitment to avoid injurious behaviors using a clinical contract not to hurt self or others provides additional information as to the actual level of distress for the subject (e.g., should the subject escalate, we have information that we need to re-think the level of

distress for the subject and to consider activating procedures to ensure physical safety). While it is possible (but highly unlikely) that a subject would misrepresent his distress by misleading clinical staff and by agreeing to engage the no suicide/no homicide contract and then kill himself or kill someone else, it remains that suicide/homicide are low base rate behaviors and the clinical evaluation and contracting process remain the gold standard for addressing highly distressed subjects in clinical practice.

- 3) A trained staff member **will remain with the participant at all times** during assessment/ treatment until a Study Clinician deems the subject not at risk or the subject is handed off to another licensed clinician.
- 4) It is possible that a subject may provide misleading information to the clinic staff members about his distress level and/or his intent to hurt himself or another. The procedures detailed here provide the best and most consistent methods used in clinical practice to respond to subjects in distress and their intentions to hurt themselves or others.

